#### Amendment 1 (version 2.0), 04-Feb-2021

The 03-Sep-2020 amendment was principally undertaken to include the dosing regimen, to specify that C-reactive protein will be measured at the same time as serum AAT, and to clarify procedures affected by and/or implemented to address the COVID-19 pandemic.

This amendment is considered to be substantial based on the criteria set forth in Article 10(a) of Directive 2001/20/EC of the European Parliament and the Council of the European Union.

The table below summarizes all changes in Version 2.0 from Version 1.0.

Description of Change	Brief Rationale	Affected Sections

 
Updated dosage and other information relating to the IMP
 
Replace "DCR-A1AT" with the a opte name "belcesiran"
 
Specified the dosage of belcesiran to be administered in the study (210 mg [1.2 mL injection volume] once every 4 weeks).
 
Clarified that the dosage of belcesiran is expressed in terms of the free-acid form of the drug substance.
 
	
 
The INN was recently adopted
 
The dosage was determined by modeling and simulation of PK/PD data from an interim analysis of Study DCR-A1AT-101 and was affirmed by the SRC and DSMC.
 
The US Pharmacopeia states that when the active ingredient in a drug product is a salt, the strength should be expressed in terms of the active moiety rather than salt strength equivalent.
 
	
 
1.1 Synopsis
 
1.2 Schema
 
2.2.5 Summary
 
2.3.3 Risk Assessment
 
4.1 Overall Study Design
 
4.3 Justification for Dose
 
6.1 Study Intervention(s) Administered
 
6.1.1 Dose Level
 
6.2 Preparation/Handling/ Storage/Accountability
 

• Removed lot number of IMP from table of study interventions	• More than one lot number may be used in the study	Belcesiran name change - throughout the protocol
Provided separate Schedules of Activities for Cohort 1 and Cohort 2	Ease of interpretation	1.3 Schedules of Activities
Specified that C-reactive protein will be measured at the same time as all serum AAT protein concentrations, and that any AAT concertation that is accompanied by a CRP value above the upper limit of normal will be repeated.	C-reactive protein and A1AT are both acute-phase proteins released into the plasma in response to inflammatory stimuli. Concomitant assessment of CRP and A1AT will allow discern between elevations in A1AT due to inflammatory stimuli or to study intervention.	
 
Schedules of Activities
 
Repeated Screening Tests
 
Repeated Screening T

Description of Change	Brief Rationale	Affected Sections

 
Addressed the impact of COVID-19:
 
All prospective participants must have a negative test for SARS-CoV-2 at the time of randomization
 
Any participant testing positive for SARS-CoV-2 will be discontinued from study intervention
 
Telehealth and/or home nursing visits may be employed if participants are unable to return to the site due to COVID-19 restrictions
 
Vaccine administration should be separated by 7 days from administration of study intervention
 
Added a statement to note that any participant with a serum AAT protein concentration that has not returned
 
	
 
To ensure that randomized participants do not have COVID-19
 
To decrease the risk for decline in pulmonary function that could arise from concomitant infection with SARS-CoV-2
 
To enable participant to continue study participant during the pandemic
 
To enable differentiation of potential AEs due to the vaccine from those due to study intervention
 
To ensure that long-term follow-up of participants occurs within a sponsored study protocol.
 
	
 
1.3 Schedules of Activities
 
4.1 Overall Study Design
 
5.2 Exclusion Criteria
 
6.5.1 Rescue Medication
 
6.5.2 COVID-19 Vaccine
 
7.1.1.2 Positive SARS-CoV-2 Test
 
7.2 Participant Discontinuation/Withdrawal from Study
 
10.2 Clinical Laboratory Tests
 
10.5 Abbreviations
 
1.1 Synopsis
 
1.3 Schedules of Activities
 

to $\ge$ 80% of Baseline by Week 48 of con itional follow-up will be followed in a separate study.		
 
2.2.4 Clinical Overview
 
4.1 Overall Study Design
 
4.4 End of Study Definition
 
8.1.1.2 Conditional Follow-up
 
8.3.1 Time Period and Frequency for Event Assessment
 

Updated clinical laboratory tests to be performed during 
 
the conditional follow-up period
 
Screening
 
	
 
Increased participant safety
 
Removed tests that are now scheduled to be assessed on an ongoing basis and corrected typographical errors in version 1.0
 
	

1.3 Schedules of Activities

8.1.1.2 Conditional Follow-up

8.2.1 Screening Assessments

10.2 Clinical Laboratory Tests

Updated description of indirect, noninvasive fibrosis blood biomarker panel, and added 3 analytes to be collected.	The trademarked LabCorp FibroSure test will not be performed as previously specified. The Sponsor will calculate the fibrosis score from the individual components of the panel.	

8.1.3.1 Biochemical Fibrosis Index

10.2 Clinical Laboratory Tests

Description of Change	Brief Rationale	Affected Sections
Added section describing the determination of hepatic Z-AAT protein content	Not previously included	8.1.2.4 Hepatic Z-AAT Content
Stated that SAEs will be collected until 30 days after the last day of study participation or until serum AAT protein concentration is <math>\geq</math> 80% of baseline on 2 consecutive visits, whichever is longer .	To ensure that participants are followed for occurrence of SAEs for a sufficient period of time.	

1.3 Schedules of Activities

8.3.1 Time Period and Frequency for Event Assessment

Updated DLCO criteria in the individual participant stopping rules. The absolute change in DLCO was lowere to $\geq 6.5$ m /min/mmHg from $\geq 8$ mL/min/mmHg	Increased participant safety	7.1.1.3 Decline in Pulmonary Function
Clarified that the duration of the conditional follow-up period is up to 48 weeks, not 12 months	Greater accuracy	
 
Synopsis
 
Schedules of Activities
 
Clinical Overview
 
Overall Study Design
 
End of Study Definition
 
State Conditional Follow-up
 

Clarified that the intensity of all AEs will be graded in accordance with CTCAE v 5.0	A "mil /mo erate/severe" rating scale is not needed in addition to CTCAE grading	10.3.4. Recording and Follow-Up of AE and/or SAE
Added a statement of statistical power	Previously not included	1.1Synopsis9.1Randomization and Sample Size
Updated language to specify the nature, number, and timing of the interim analyses	To clarify that one interim futility analysis will be performed and that additional analyses to support composite endpoint determination may be performed.	9.4 Interim Analyses
Added steatosis scores as an endpoint	Previously missing in the tables of Objectives and Endpoints	
 
Synopsis
 
Objectives and Endpoints
 

Removed determination of PK in urine	No longer needed in Phase 2	
 
Synopsis
 
Schedules of Activities
 
Objectives and Endpoints
 
Overall Study Design
 
Pharmacokinetics
 

Description of Change	Brief Rationale	Affected Sections
--	---	--
		8.5.1Metabolite Identification9.3.2.1Pharmacokinetic Analyses
Specified that blood pressure and ECG readings are to be conducted in the sitting rather supine position and that only 5 minutes of rest (not 10 minutes) are required	Consistency with clinical practice	

5.2 Exclusion Criteria

8.2.3 Vital Signs Measurements

8.2.4 Electrocardiograms

Removed clarification that heart rate will be taken from the ECG when the ECG and vital signs are recorded at the same time and added ventricular rate and RR to the list of parameters to be recorded via ECG.	To better align with electronic data outputs	
 
Schedules of Activities
 
Vital Signs Measurements
 
Electrocardiograms
 

Updated interval for rescreening due to exacerbations of underlying lung disease from 2 to 3 months	To ensure that participants have stable lung function at the time of enrollment.	

5.2 Exclusion Criteria

5.4 Screen Failures

Removed Medical Monitor approval of restricted concomitant medications	Ad hoc approval is inconsistent with intent of restrictions	6.5 Concomitant Medications
Updated units of measure for DLCO to mL/min/mmHg	Consistency across protocol	8.2.5.2 Diffusion Capacity of the Lungs for Carbon Monoxide
Removed language requesting that the Investigator to make every effort to contact the medical monitor prior to unblinding in case of medical emergency.	The decision to unblind in an emergency belongs solely to the Investigator.	6.3 Measures to Minimize Bias: Randomization and Blinding
Deleted Heading 8.8 Biomarkers. Promoted Heading 8.8.1 Immunogenicity Assessments to 8.8	Consistency with protocol template	8.8 Biomarkers-Immunogenicity Assessments
Updated the acronyms for alpha-1 antitrypsin deficiency and alpha-1 antitrypsin deficiency-associated liver disease	To conform with new style guide	Throughout the protocol
Administrative updates	Updated personnel, updated Sponsor corporate address, updated reference and abbreviation lists, and other minor corrections	Cover Page, Sponsor Signature Page, References, Abbreviations, and throughout the protocol

FEV ₁	Forced expiratory volume in one second
FVC	Forced vital capacity
IVRS/IWRS	Interactive Voice/Web Response System
MedDRA	Medical Dictionary for Regulatory Activities
PD	Pharmacodynamic(s)
PE	Physical examination
PFT	Pulmonary function test(s)
PiZZ	Autosomal homozygous mutant AAT Z-allele genotype
PK	Pharmacokinetic(s)
SAE	Serious adverse event
SAP	Statistical Analysis Plan
SD	Standard deviation
SDTM	Study Data Tabulation Model
SoA	Schedule of Activities
TEAE	Treatment-emergent adverse event
TFL	Tables, figures, listings
ULN	Upper limit of normal
WHO	World Health Organization

1 INTRODUCTION

The purpose of this Statistical Analysis Plan (SAP) is to provide a description of the statistical methods to be implemented for the analysis of study data from protocol DCR-A1AT-201, “A Phase 2, Randomized, Double-blind, Placebo-controlled Study Investigating Safety, Tolerability, Pharmacokinetics and Pharmacodynamics of Two Dose Levels of Belcesiran in Patients with Alpha-1 Antitrypsin Deficiency-Associated Liver Disease”. The SAP will be finalized prior to the final database lock. Any deviations from the SAP after database lock will be documented in the final Clinical Study Report (CSR).

The SAP reflects the planned study design as per the latest version of the protocol; however, the Sponsor made the decision to stop the trial prior to the enrollment of Cohort 3 subjects and prior to the completion of the planned study procedures for Cohorts 1 and 2 participants. Cohort 3 and related activity plan will be cancelled. Therefore, the available safety, AAT and biopsy data from Cohort 1 and Cohort 2 will be analyzed for the CSR purpose and there is no analysis planned for Cohort 3.

2 STUDY OVERVIEW

2.1 Study Objectives

2.1.1 Primary Objective

The primary objectives are:

- To evaluate the safety and tolerability of multiple doses of belcesiran in patients with alpha-1 antitrypsin deficiency-associated liver disease (AATLD) for Cohorts 1 and 2.
- To characterize the pharmacodynamics (PD) of belcesiran in patients with AATLD for Cohorts 1, 2, and 3.

2.1.2 Secondary Objectives

The secondary objectives are:

- To characterize the pharmacokinetics (PK) of belcesiran in the plasma of patients with AATLD.
- To assess the effect of belcesiran on liver histology in patients with AATLD.

2.1.3 Exploratory Objectives

The exploratory objectives are:

- To assess the effect of belcesiran on liver stiffness in patients with AATLD.
- To assess the effect of belcesiran on liver fibrosis and/or inflammation in patients with AATLD.

2.2 Study Design

2.2.1 Overview

The study is a multiple dose, randomized, placebo-controlled, double-blind study to evaluate the safety, tolerability, PK, and PD of 2 dose levels of belcesiran in adult patients with PiZZ AATLD (liver fibrosis F1, F2, F3, or F4, METAVIR scoring system).

After the screening period, Participants will be randomized, and administration of IMP (investigational medicinal product) will be initiated. Participants will return to the site for administration of IMP and safety, tolerability, PK, and PD monitoring at specified time points as per the schedule of activities (SoA) through the end of treatment (EOT) visit. If participants are not able to return to the site for assessments or

procedures, visits may be conducted by qualified medical professionals as at-home telemedicine and/or home nursing visits, at the discretion of the Investigator.

The study will be conducted in 3 separate cohorts. Participants will be randomized in a 1:1 fashion to either Cohort 1 or 2. Once Cohort 1 and 2 have enrolled, enrollment of Cohort 3 will be initiated.

- Participants in Cohort 1 (N=8) will be randomized 3:1 to either belcesiran 210 mg or placebo and a liver biopsy will be performed at week 24 to assess the effect of belcesiran. In addition, participants will have the option to continue treatment for an additional 72 weeks for a total treatment duration of 96 weeks.
- Participants in Cohort 2 (N=8) will be randomized 3:1 to either belcesiran 210 mg or placebo and a liver biopsy will be performed at week 48 to assess the effect of belcesiran. In addition, participants will have the option to continue treatment for an additional 48 weeks for a total treatment duration of 96 weeks.
- Participants in Cohort 3 (N=30) will be randomized 2:1:2:1 to belcesiran 210 mg, the equivalent amount of placebo for belcesiran 210 mg, belcesiran 50 mg or the equivalent amount of placebo for belcesiran 50 mg. Participants will be blinded within each dose level. Participants will have a liver biopsy performed at week 24 to assess the effect of belcesiran and thereafter continue treatment until 96 weeks of treatment have been completed.

Randomization will be stratified based on fibrosis stage (METAVIR Score F1/F2, F3 or F4) in all cohorts.

Participants in Cohort 1 and 3 will receive monthly dosing for the first 24 weeks and then shift to quarterly dosing thereafter until week 96. Participants in Cohort 2 will receive monthly dosing for the first 48 weeks and then shift to quarterly dosing thereafter until week 96. Participants will continue the IMP throughout the study, unless the participant or investigator decide to discontinue IMP, or the participant withdraws from the trial, or a discontinuation criterion is met.

All Participants in Cohorts 1 to 3 will have the option to undergo a liver biopsy at EOT/week 96. The biopsy at 96 weeks will inform about Z-AAT levels and provide further information about possible improvements in liver histology. Biopsy findings will be correlated with changes in non-invasive markers of liver disease and liver stiffness.

After the EOT visit, all participants will be followed up for 48 weeks. If a participant in Cohorts 1 and 2 does not wish to extend the treatment period to 96 weeks, they will proceed to the 48-week follow-up period instead.

The trial will be monitored by an independent external data safety monitoring committee (DSMC). The DSMC will review accumulating data from the trial in an unblinded fashion to ensure adequate monitoring of safety. The timing and scope of the review meetings will be defined in the DSMC charter.

Figure 1: Dose Regimens by Cohort

Cohort 1					Cohort 2					Cohort 3						
	Visit #	Dose #	Day	Week		Visit #	Dose #	Day	Week		Visit #	Dose #	Day	Week		
Treatment Period	1	1	1		Treatment Period	1	1	1		Treatment Period	1	1	1			
	2		2			2		2			2		2		2	
	3		3			3		3			3		3		3*	
	4		15			4		15			4		15*		15*	
	5	2	29			5	2	29			5	2	29		29	
	6		30			6		30			6		30*		30*	
	7	3	57			7	3	57			7	3	57		57	
	8	4	85			8	4	85			8	4	85		85	
	9	5	113			9	5	113			9	5	113		113	
	10	6	141			10	6	141			10	6	141		141	
	11	7	169	24		11	7	169	24		11	7	169	24	169	24
Optional Treatment Period	12		211*		Optional Treatment Period	12	8	197		Optional Treatment Period	12		211*			
	13	8	253			13	9	225			13	8	253			
	14		295*			14	10	253			14		295*			
	15	9	337	48		15	11	281			15	9	337	48		
	16	10	421			16	12	309			16	10	421			
	17	11	505	72		17	13	337	48		17	11	505			
	18	12	589			18	14	421			18	12	589			
	19	13	673	96		19	15	505	72		19	13	673	96		
Follow-up Period	18		757		Optional Treatment Period	20	16	589		Follow-up Period	20		757			
	19		841	120		21	17	673	96		21		841	120		
	20		925			22		757			22		925			
	21		1009	144		23		841	120		23		1009	144		
	22		1177			24		925			24		1009	144		
	23		1345	192		25		1009	144		25		1177			
Required Dosing Visits in yellow Optional Dosing Visits in blue Follow-up visits in gray * Phone visit																

2.2.2 Randomization and Blinding

The study is a randomized, placebo-controlled, double-blind study, where the Investigator and the participants are blinded to IMP and placebo. All sites will have unblinded staff responsible for preparing IMP. A subset of the Sponsor’s study team will be unblinded. Details of unblinding, including the list of unblinded Sponsor team members, will be captured in the Study Blinding Plan.

All participants will be centrally assigned to randomized study intervention using an Interactive Voice/Web Response System (IVRS/IWRS). Before the study is initiated, directions for the IWRS will be provided to each site.

Investigators will remain blinded to each participant’s assigned study intervention throughout the course of the study. To maintain this blind, the unblinded site staff will be responsible for the preparation and dispensing of all study intervention and will endeavor to ensure that there are no differences in the time taken to dispense the study intervention following randomization. Additionally, the unblinded site staff will affix a translucent label over the syringe(s) to mask the contents.

The unblinded study monitor and any auditors present in the event of a Quality Assurance or a competent authority audit will be allowed access to unblinded study intervention records at the site(s) to verify that randomization/dispensing has been done accurately and per protocol and the Pharmacy Manual.

In case of an emergency, the Investigator has the sole responsibility for determining if unblinding of a participant’s treatment assignment is warranted. Participant safety must always be the first consideration in making such a determination. If a participant’s treatment assignment is unblinded, the Medical Monitor must be notified within 24 hours after breaking the blind. The date and reason that the blind was broken must be recorded in the source documentation.

Potentially unblinding study results, such as the serum AAT protein concentrations, will not be shared with blinded study participants and site personnel during the treatment period.

Study intervention will be administered at the investigational site. The planned dose, actual administered dose, and injection date and time will be recorded on the appropriate electronic case report form (CRF).

2.2.3 *Study Drug*

Belcesiran is supplied as a solution of the drug substance (belcesiran sodium) in water for injection.

2.2.4 *Sample Size Determination*

The study will include 3 cohorts. In Cohorts 1 and 2 there will be up to 8 participants in each cohort (randomization scheme ratio of 3:1 active: placebo). The sample size for Cohort 1 and Cohort 2 is based on clinical consideration rather than statistical power calculation.

The primary endpoint for Cohort 3 of this study is the percentage change from baseline in serum and liver Z-AAT protein concentration at week 24. Assuming the percentage change from baseline is 80%, 60% and 10% in the active high dose group, active low dose group and placebo group respectively, and the standard deviation is 0.5 for all three groups, a sample size of 10 participants per treatment group will provide at least 80% power to detect a statistically significant difference between active high dose group and placebo, and between active low dose group and placebo, at an overall 1-sided significance level of 0.05.

The F1/F2, F3, and F4 fibrosis types will be used as randomization stratification factors for all 3 cohorts.

2.3 **Study Endpoints**

2.3.1 *Primary Endpoints*

The primary endpoints for Cohorts 1 and 2 are:

- The incidence and nature of treatment emergent adverse events (TEAEs), and the change from Baseline in pulmonary function tests (PFTs), 12-lead electrocardiograms (ECGs), physical examination (PE) findings, vital signs, and clinical laboratory tests
- Changes from baseline to weeks 24 (Cohort 1)/ 48 (Cohort 2) in serum AAT protein concentrations

The primary endpoints for Cohort 3 are:

- Change from baseline to week 24 in serum AAT protein levels
- Change from baseline to week 24 in liver AAT protein levels

2.3.2 *Secondary Endpoints*

The secondary endpoints are:

- PK profile of belcesiran
- Change from baseline up until week 96 in liver fibrosis
- Change from Baseline up until week 96 in diastase-resistant PAS-positive AAT globules

2.3.3 *Exploratory Efficacy Endpoints*

The exploratory endpoints are:

- Change from Baseline up until week 96 in FibroScan® score
- Change from Baseline up until week 96 in enhanced liver fibrosis (ELF) score
- Change from Baseline up until week 96 in cytokeratin 18 (CK-18)

3 STATISTICAL METHODOLOGY

3.1 General Considerations

3.1.1 Analysis Day

Analysis day will be calculated from the date of first dose of study drug. The day of the first dose of study drug will be Day 1, and the day immediately before Day 1 will be Day -1. Note that for analysis purpose there will be no Day 0.

3.1.2 Analysis Visits

Scheduled visits will be assigned to analysis visits as recorded on the CRF. Unscheduled visits recorded on the CRF will not be re-assigned and will remain labeled as unscheduled.

Early termination (ET) visits for Cohort 1 participants will be assigned to analysis visits according to the following visit windows if participants enter the optional treatment period:

Analysis Visit	Target Analysis Day	Low Analysis Day	High Analysis Day
Screening	-35		-1
Day 1	1	1	1
Day 2	2	2	2
Day 3	3	3	9
Day 15	15	10	22
Day 29	29*	23	43
Day 57	57	44	71
Day 85	85	72	99
Day 113	113	100	127
Day 141	141	128	155
Day 169	169	156	183
Day 211	211	184	232
Day 253	253	233	274
Day 295	295	275	316
Day 337	337	317	379
Day 421	421	380	463
Day 505	505	464	547
Day 589	589	548	631
Day 673	673	632	715
Day 757- Post EOT Week 12	757	716	799
Day 841-Post EOT Week 24	841	800	883
Day 925- Post EOT Week 36	925	884	967
Day 1009- Post EOT Week 48	1009	968	1093
Day 1177- Post EOT Week 72	1177	1094	1261
Day 1345- Post EOT Week 96	1345	1262	

* Day 30 will always be the day after Day 29, regardless of when Day 29 occurs.

Early termination (ET) visits for Cohort 1 participants will be assigned to analysis visits according to the following visit windows if participants do not enter the optional treatment period:

Analysis Visit	Target Analysis Day	Low Analysis Day	High Analysis Day
Screening	-35		-1
Day 1	1	1	1
Day 2	2	2	2
Day 3	3	3	9
Day 15	15	10	22
Day 29	29*	23	43
Day 57	57	44	71
Day 85	85	72	99
Day 113	113	100	127
Day 141	141	128	155
Day 169	169	156	211
Day 253- Post EOT Week 12	253	212	295
Day 337- Post EOT Week 24	337	296	379
Day 421- Post EOT Week 36	421	380	463
Day 505- Post EOT Week 48	505	464	589
Day 673- Post EOT Week 72	673	590	757
Day 841- Post EOT Week 96	841	758	

* Day 30 will always be the day after Day 29, regardless of when Day 29 occurs.

Early termination visits for Cohort 2 participants will be assigned to analysis visits according to the following visit windows if participants enter the optional treatment period:

Analysis Visit	Target Analysis Day	Low Analysis Day	High Analysis Day
Screening	-35		-1
Day 1	1	1	1
Day 2	2	2	2
Day 3	3	3	9
Day 15	15	10	22
Day 29	29	23	43
Day 57	57	44	71
Day 85	85	72	99
Day 113	113	100	127
Day 141	141	128	155
Day 169	169	156	183
Day 197	197	184	211
Day 225	225	212	239
Day 253	253	240	267
Day 281	281	268	295
Day 309	309	296	323

Day 337	337	324	379
Day 421	421	380	463
Day 505	505	464	547
Day 589	589	548	631
Day 673	673	632	715
Day 757- Post EOT Week 12	757	716	799
Day 841- Post EOT Week 24	841	800	883
Day 925- Post EOT Week 36	925	884	967
Day 1009- Post EOT Week 48	1009	968	1093
Day 1177- Post EOT Week 72	1177	1094	1261
Day 1345- Post EOT Week 96	1345	1262	

Early termination visits for Cohort 2 participants will be assigned to analysis visits according to the following visit windows if participants do not enter the optional treatment period:

Analysis Visit	Target Analysis Day	Low Analysis Day	High Analysis Day
Screening	-35		-1
Day 1	1	1	1
Day 2	2	2	2
Day 3	3	3	9
Day 15	15	10	22
Day 29	29	23	43
Day 57	57	44	71
Day 85	85	72	99
Day 113	113	100	127
Day 141	141	128	155
Day 169	169	156	183
Day 197	197	184	211
Day 225	225	212	239
Day 253	253	240	267
Day 281	281	268	295
Day 309	309	296	323
Day 337	337	324	379
Day 421- Post EOT Week 12	421	380	463
Day 505- Post EOT Week 24	505	464	547
Day 589- Post EOT Week 36	589	548	631
Day 673- Post EOT Week 48	673	632	757
Day 841- Post EOT Week 72	841	758	925

Day 1009- Post EOT Week 96	1009	926	
-------------------------------	------	-----	--

If the activity is not scheduled to occur at the assigned visit, then the closest scheduled visit for that activity will be assigned. If an ET visit is re-assigned to an analysis visit for which a scheduled visit occurred, then the data from the scheduled visit will be used in the analysis for that time point. For example, if the Dose #4/Day 85 visit occurred as scheduled and then a participant withdrew on Day 90 and came back in for ET assessments, the ET visit will be re-assigned to Day 85 based on the table above; however, the assessments from the scheduled Day 85 visit will be used for analysis of the Day 85 time point.

In addition, the measurements from all last visits will be summarized descriptively for all safety assessments.

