5.2 Final Analysis

The study was terminated prior to enrolling the participants into Cohort 3. The database will be locked after completion of the follow-up for Cohort 1 and Cohort 2 participants. The study will be unblinded at the participant level and the final analysis will be generated. The final analysis will be performed on all available data as described in the above sections of SAP. The corresponding tables, figures, and listings (TFL) will be provided after the database lock.

In addition to TFLs, Study Data Tabulation Model (SDTM) data and ADaM data along with associated files will be provided. Associated files may include the following: annotated CRFs, SDTM specifications, SDTM programs, ADaM specifications, ADaM programs, and TFL programs.

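### For participants who enter the optional period, SAP 3.1.2 fixes EOT at Day 673, so an early-termination visit in a follow-up that began sooner gets a treatment-period label up to Day 715 and a too-early post-EOT label after that

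*SAP*

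**What the plan says.** SAP 3.1.1 sets the time origin: "Analysis day will be calculated from the date of first dose of study drug". SAP 3.1.2 then separates two kinds of visit. For scheduled visits, "Scheduled visits will be assigned to analysis visits as recorded on the CRF". Only ET visits are windowed by study day, and each cohort has two tables: one for participants who stay out of the optional period (EOT Day 169 in Cohort 1, Day 337 in Cohort 2) and one for those who enter it, whose ET visits "will be assigned to analysis visits according to the following visit windows if participants enter the optional treatment period".

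In both extender tables the last treatment window is Day 673 (Days 632 to 715). The first post-EOT row is "Day 757- Post EOT Week 12", covering Days 716 to 799. No rule refers to the day on which the participant actually reached EOT.

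Two further rules in 3.1.2 matter. On precedence: "If an ET visit is re-assigned to an analysis visit for which a scheduled visit occurred, then the data from the scheduled visit will be" the record analysed. On assessments: "If the activity is not scheduled to occur at the assigned visit, then the closest scheduled visit for that activity will be assigned".

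SAP 1 records that the sponsor stopped the trial "prior to the completion of the planned study procedures for Cohorts 1 and 2 participants", and SAP 5.2 adds: "The database will be locked after completion of the follow-up for Cohort 1 and Cohort 2 participants". Protocol Table 5 schedules follow-up by weeks after EOT and includes an ET column.

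**The concern.** The extender table is right only for someone whose EOT was at Day 673. The SAP was written knowing that the trial had been stopped early, so some extenders may have entered follow-up before that day. If one of them then terminated follow-up, the ET visit would be placed by days since first dose and could land on a dosing visit that the participant never reached.

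The precedence rule cannot correct this. It displaces ET data only when the scheduled visit of that name took place, and for this participant the later dosing visit did not. The cell is empty, and the off-drug value would fill it.

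At stake are the by-visit summaries of serum AAT (SAP 3.4.1, which also plots all study periods), PFTs (3.7.2) and laboratory tests (3.7.3). An off-drug value in a late treatment row could blur the apparent knockdown, or be read as an on-drug safety value.

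**Working it through.** **Reproducing the plan's figures.** Post-EOT target day = EOT day + 7 × week. With EOT = 673:
- Week 12: 673 + 84 = 757
- Week 24: 673 + 168 = 841
- Week 36: 673 + 252 = 925
- Week 48: 673 + 336 = 1009
- Week 72: 673 + 504 = 1177
- Week 96: 673 + 672 = 1345

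All six match both extender tables, so EOT is fixed at Day 673. The non-extender tables reproduce in the same way with EOT = 169 and 337.

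**Moving EOT earlier.** The documents give no actual stop dates, so I assume EOT at each optional dosing day before Day 673: Days 253 and 337 (Cohort 1 only), and Days 421, 505 and 589 (both cohorts). The label is read from the printed extender windows.

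| Actual EOT | True Week 12 | True Week 24 | True Week 36 | True Week 48 |
|---|---|---|---|---|
| Day 253 | Day 337 | Day 421 | Day 505 | Day 589 |
| Day 337 | Day 421 | Day 505 | Day 589 | Day 673 |
| Day 421 | Day 505 | Day 589 | Day 673 | Post EOT Week 12 |
| Day 505 | Day 589 | Day 673 | Post EOT Week 12 | Post EOT Week 24 |
| Day 589 | Day 673 | Post EOT Week 12 | Post EOT Week 24 | Post EOT Week 36 |

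**Share of follow-up days affected.** Over 48 weeks (336 days), the share with a treatment-period label is (715 − EOT day)/336, capped at 100%:
- Day 253 or 337: 100%, because follow-up ends on Day 589 or 673
- Day 421: 294/336 = 87.5%
- Day 505: 210/336 = 62.5%
- Day 589: 126/336 = 37.5%

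Part of this is by design. Even with EOT at Day 673, Days 674 to 715 carry the EOT visit's own label (42/336 = 12.5%). Removing the days that fall in the participant's own EOT window leaves those labelled as a later dosing visit that the participant never reached:
- Day 253: 273/336 = 81.25%; a further 42 days (12.5%) map to the Day 295 phone visit, and their data pass to the nearest visit with that assessment
- Day 337: 294/336 = 87.5%
- Day 421: 252/336 = 75%
- Day 505: 168/336 = 50%
- Day 589: 84/336 = 25%

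Within 48 weeks, every day after Day 715 gets a post-EOT label that is too early. Protocol 4.1 gives Cohorts 1 and 2 a further 48 weeks, while SAP 2.2.1 mentions only 48. Over 96 weeks (672 days) the treatment-label shares are 68.8%, 56.2%, 43.8%, 31.2% and 18.8% for EOT at Days 253, 337, 421, 505 and 589. The rest are too early, except that with EOT at Day 589, 126 of the 672 days share the correct bin because the late bins are wide.

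**Primary time points.** The windows are Days 156 to 183 (Cohort 1, Week 24) and Days 324 to 379 (Cohort 2, Week 48). The first optional dose is at Day 253 or Day 421 respectively, so follow-up after any optional dose starts later than the primary window.

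**Possible effect on one row (assumed values).** Active participants per cohort: 8 × 3/4 = 6 at most. Suppose a late row holds three on-drug values of −80% and one off-drug value. At −20% the mean is (3 × −80 − 20)/4 = −65%; at −60% it is (3 × −80 − 60)/4 = −75%. The documents give no recovery figure, so this shows only the sensitivity of a small row.

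**The case against.** The strongest reply is that the harm may never reach a table. SAP 3.1.4 puts scheduled visits, follow-up included, in summaries and figures, and names ET data only for listings. That stands as a real doubt, but it does not settle the matter. SAP 3.1.2 decides which record is analysed at a time point when an ET visit and a scheduled visit coincide, and windowing ET visits has little purpose if they are only listed. The two sections need reconciling in any case.

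Other limits stand in full:
- Scheduled follow-up visits keep their CRF labels, and lock follows completion of follow-up, so most post-stop data are probably labelled correctly. The problem needs an extender who entered follow-up before Day 673 and then terminated it. The early stop makes this plausible; the documents do not say that it happened.
- A participant who individually stops drug is told by Protocol 7.1.1 to stay on the visit schedule. A treatment-period label is then the intended one.
- Optional doses are 84 days apart and serum AAT is drawn predose. A value 12 weeks after the last dose therefore has the same time since dosing as an ordinary predose sample in that period. The label is still wrong, but recovery should not dilute that row.
- No hypothesis tests are planned (SAP 3.1.5), and all data are listed.

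A reader might also infer that every follow-up ET visit becomes a dosing visit, or that liver-stiffness summaries are distorted. Neither is supported: labels after Day 715 are post-EOT weeks, Cohort 1 Days 211 and 295 are phone visits, and the SAP specifies no FibroScan or MRE summary.

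**Conclusion.** The concern holds in a narrow form. The extender tables give a wrong label to an ET visit made in a follow-up that began before Day 673, apart from visits soon after EOT that fall in the EOT visit's own window and some late days under 96-week follow-up. Under the assumed EOT days and 48 weeks of follow-up, 37.5% to 100% of possible ET days get a treatment-period label, and 25% to 87.5% are labelled as a later dosing visit that was never reached. These are shares of calendar days, not of participants or visits; the number of affected visits is not stated.

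The consequence is conditional on ET data entering the summaries. If they do, the risk is to late-visit serum AAT, PFT and safety rows with at most 6 active participants per cohort. A reader might infer that the primary result is biased. For extenders who took an optional dose it is not, because their follow-up cannot fall in the Week 24 or Week 48 window. The point merits correction because the rule is wrong as written for a foreseeable case and is cheap to repair.

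**What to change.** In SAP 3.1.2, for ET visits after the participant's actual EOT visit or entry into follow-up, assign the Post-EOT Week 12, 24, 36, 48, 72 and 96 bins by days since that actual EOT. Do this in all four tables, since the non-extender tables also fix EOT (Day 169 or 337). Keep days since first dose for all other ET visits, including those of participants who stopped drug but stayed on the treatment schedule under Protocol 7.1.1.

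The anchor should not be the last dose. A Cohort 1 participant last dosed on Day 85 who stayed on schedule and had an ET visit on Day 169 would become Post-EOT Week 12 (85 + 84 = 169) and drop out of the Week 24 time point.

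State in 3.1.4 whether windowed ET data enter summaries and figures, and align 3.1.2 with it. The cost is SAP wording and one derived variable (days since actual EOT); no new data are needed.
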